10.1 Sample size determination

The sample size calculation is based on the primary estimand described in Section [4.2](#).

It is expected based on phase 2 trial data (NN8640-4172) that the proportion of subjects with no landmark visit data or who discontinued randomised treatment before landmark visit is 10% with similar withdrawal reasons in the two treatment arms (5% discontinuing randomised treatment but have landmark visit data and 5% withdrawn /lost to follow up with no landmark visit data). It is expected that subjects discontinuing their randomised treatment will start on ancillary treatment, if no medical reasons prohibits this. The term “retrieved subjects” will be used in this section as a short form for “subjects discontinuing randomised treatment but have landmark visit data”.

Assuming the same proportions of subjects with no landmark visit and retrieved subjects in the two arms leads to the following sample size calculation.

Primary estimand (FDA and PMDA)

The sample size is determined using a non-inferiority margin of 1.8 cm/year and a one sided two-group t-test with a significance level of 2.5% for a 2:1 randomisation ratio between somapacitan and Norditropin®.

As trial results from trials allowing ancillary therapy or having retrieved landmark data included in the analysis are limited, a conservative standard deviation for HV at week 52 was chosen (SD=3.5cm/year) and the different scenarios giving 90% power for the primary analysis are presented in the table below under the assumption of a true difference in annualized HV of 0 cm/year between the two treatment arms and no true difference in annualized HV between retrieved subjects and subjects staying on randomised treatment at landmark visit.

Table 3 Sample size for various standard deviations

SD	3.0 cm/year	3.25 cm/year	3.5 cm/year	3.75 cm/year
Primary estimand	144	171	192	219
(Treatment policy strategy)				

The SD candidates are based on reported SD values from clinical trials [21-23](#). For sensitivity analysis a tipping point analysis is planned and based on a penalty for imputed values in the somapacitan arm of 1.8 cm/year this gives a power of 87% (adjusted treatment effect: $0.9*0 - 0.05*1.8 = -0.09$), under the assumption of 5% of subjects not having landmark visit data (corresponding to an analysis that performs an imputation under the non-inferiority null method).²⁴

Primary estimand (EMA)

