Additionally, a value $b \geq 0$ will be added to the imputed landmark visit value for Norditropin® treated subjects prior to analysis, so that the tipping point analysis also can address scenarios where withdrawals from the active comparator arm achieve greater HV than the value estimated from retrieved subjects (two-dimensional tipping point analysis).

Primary estimand (EMA)

The primary analysis of the primary endpoint addressing the alternative primary estimand Section [4.2.2](#) is based on FAS but data assessed after discontinuation of randomised treatment will be disregarded in the analysis.

In order to estimate this primary estimand (hypothetical strategy) a mixed model for repeated measurements (MMRM) with an unstructured covariance matrix is conducted on HV data (annualized HV at planned visits at week 13, 26, 39 and 52) up to discontinuation of randomised treatment for each treatment arm using all randomised subjects and assuming missing at random (MAR) for both treatment arms. The MMRM will include gender, age group, region, GH peak group and gender by age group by region interaction term as factors and baseline height as a covariate, all nested within week as a factor.

From this analysis an estimate of the treatment difference at week 52 with corresponding 95% CI and p-value will be presented.

Non-inferiority of somapacitan will be considered confirmed if the lower boundary of the two-sided 95% confidence interval is above -1.8 cm/year or equivalent if the p-value for the one-sided test of

$H_0: D \leq -1.8$ cm/year vs $H_A: D > -1.8$ cm/year is less than 2.5 %, where D is the mean treatment difference (somapacitan – Norditropin[®]). If non-inferiority is confirmed, superiority will be considered confirmed if the lower boundary of the two-sided 95% confidence interval is above 0 cm/year. If superiority is confirmed, the p-value from the two-sided superiority test will also be reported.

A tipping point analysis will be conducted as a sensitivity analysis for the analysis of the primary endpoint for the primary estimand described above (hypothetical strategy). For this analysis, the missing data are expected to be mainly due to subjects that are withdrawn from the trial or discontinue randomised treatment. The sensitivity analyses described below will be used to investigate whether the results from the primary analysis are robust against departures from the assumption of MAR.

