Let δ be defined as the difference between the mean of the observed data and the mean of the unobserved data $\mu_{obs} - \mu_{unobs}$, adjusted for other observed data. Under an MAR analysis, δ is assumed to be 0. Positive values of δ indicate that subjects with missing endpoint values have smaller HV than subjects with observed endpoint values. If subjects primarily withdraw or discontinue randomised treatment due to a perceived lack of efficacy then this could be the most likely direction of departure from MAR. Let f_1 and f_0 be the fractions of subjects with unobserved endpoint data in the somapacitan and Norditropin[®] arms, respectively. The sensitivity analysis is done by subtracting a quantity Δ from the treatment effect estimate under the MAR assumption, where $\Delta = f_1\delta$ if data depart from MAR in the somapacitan arm only, $\Delta = -f_0\delta$ if data depart from MAR in the Norditropin[®] arm only, and $\Delta = (f_1 - f_0)\delta$ if data depart from MAR in the same way in both arms. The calculations for the 3 scenarios will use a range of δ values increasing from 0 until the resulting 95% CI no longer is completely above -1.8cm/year for the most conservative evaluation (data depart from MAR in the somapacitan arm only) and the approximation that the standard error of the treatment difference is unaffected by the sensitivity analysis²⁵. All subjects from the FAS can be viewed as included in this analysis as subjects with missing endpoint data will be contributing to one of the fraction values f_1 and f_0 .

An analysis of the primary endpoint using the same analysis model as was used for the primary analysis under the primary estimand (hypothetical strategy) but based on PP instead of FAS will be conducted as a supplementary analysis.

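### The EMA tipping-point analysis never examines missing Norditropin children growing more than observed ones, so two of its three scenarios cannot challenge non-inferiority within the planned range

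*Combined protocol and SAP*

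**What the plan says.** For the EMA (hypothetical) estimand, section 10.3.1 disregards data collected after discontinuation of randomised treatment and fits an MMRM under MAR. The tipping-point analysis then defines δ as the observed mean minus the unobserved mean, so positive δ means that missing children grow less. It subtracts Δ from the treatment difference and keeps the standard error fixed. With f1 and f0 the unobserved fractions in the somapacitan and Norditropin arms, the scenarios are:

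- somapacitan arm departs: Δ = f1·δ
- Norditropin arm departs: Δ = -f0·δ ("if data depart from MAR in the Norditropin[®] arm only, and")
- both arms depart in the same way: Δ = (f1 - f0)·δ

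δ starts at 0 and increases until the 95% CI is no longer wholly above -1.8 cm/year "for the most conservative evaluation (data depart from MAR in the somapacitan arm only"). The positive direction is supported by a conditional argument: it could be the likeliest one if children mainly stop because of perceived lack of efficacy.

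For the FDA/PMDA estimand, the same section penalises imputed somapacitan values by c > 0 and also adds b ≥ 0 to imputed Norditropin values. The stated purpose is to cover "scenarios where withdrawals from the active comparator arm achieve greater HV than the value estimated from retrieved subjects (two-dimensional tipping point analysis").

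**The concern.** Non-inferiority is threatened from two sides: missing somapacitan children may do worse than MAR predicts, or missing Norditropin children may do better. With one δ that is never negative, the EMA scenarios reach only the first. Two of the three lines are then favourable or neutral because of their algebra, and a reader of the report could take them as evidence of robustness.

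The gap falls where missing data matter more. Section 10.1 expects 5% of children to discontinue but have landmark data and 5% to have none. The FDA/PMDA analysis lacks only the second group. The EMA analysis sets aside the post-discontinuation data of the first group as well, so about 10% is unobserved.

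**Working it through.** **Inputs (section 10.1).** Margin 1.8 cm/year; "a one sided two-group t-test with a significance level of 2.5% for a 2:1 randomisation ratio between somapacitan and Norditropin"; "a conservative standard deviation for HV at week 52 was chosen (SD=3.5cm/year"); power evaluated "under the assumption of a true difference in annualized HV of 0 cm/year between the two treatment arms". The share with "no landmark visit data or who discontinued randomised treatment before landmark visit is 10% with similar withdrawal reasons in the two treatment arms". The calculation proceeds "Assuming the same proportions of subjects with no landmark visit and retrieved subjects in the two arms", so f1 = f0 = 0.10 for EMA. N = 192 at 2:1 gives 128 and 64; less 10%, 115.2 and 57.6.

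**Reproducing the plan's figure.** Noncentral-t power with 115.2 and 57.6, SD 3.5, margin 1.8 and true difference 0 is 88.7%. The plan states 88% for EMA at N = 192, so the inputs are read correctly. The plan gives no tipping value to reproduce.

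**Starting point at an estimate of 0.**

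- SE = 3.5·√(1/115.2 + 1/57.6) = 0.565
- Lower 95% limit = 0 - 1.974 × 0.565 = -1.115
- Room to the margin R = -1.115 + 1.8 = 0.685

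The result tips when Δ reaches R.

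**Somapacitan only.** f1·δ = R gives δ = 0.685/0.10 = 6.85 cm/year. This is where the planned range ends.

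**Norditropin only.** Δ = -f0·δ ≤ 0 for every δ ≥ 0. At δ = 6.85 the lower limit rises from -1.115 to -1.115 + 0.685 = -0.43. It cannot cross -1.8 if the primary analysis did not.

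**Equal departure.** With f1 = f0, Δ = 0 at every δ. In general, at the end of the range δ = R/f1, so Δ = R·(f1 - f0)/f1. That is below R whenever f0 > 0. Example: with f1 = 0.10 and f0 = 0.05 the scenario would tip at 0.685/0.05 = 13.7, but the range stops at 6.85, where the limit is about -1.46. Only f0 = 0 lets it tip within range; with 10% missing among 64 children the chance of that is 0.9^64 ≈ 0.1%.

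**Ranking of the three.** For every δ ≥ 0, f1·δ is at least (f1 - f0)·δ and at least -f0·δ. Somapacitan-only is the harshest of the listed scenarios.

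**The direction not examined.** Let missing somapacitan children be worse by d and missing Norditropin children better by d. Then Δ = (f1 + f0)·d, which tips at d = 0.685/0.20 = 3.43. A Norditropin departure alone tips at δ = -6.85.

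| Assumed estimate, SD | Somapacitan only | Opposite, per arm | Norditropin only |
|---|---|---|---|
| 0, SD 3.5 | 6.85 | 3.43 | -6.85 |
| -0.5, SD 3.5 | 1.85 | 0.93 | -1.85 |
| 0, SD 3.0 | 8.44 | 4.22 | -8.44 |

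**Across simulated trials** (200,000; 10% missing per arm on average, SD 3.5, true difference 0), among those confirming non-inferiority the median tipping value is 7.7 cm/year for somapacitan only and 3.9 per arm for opposite departures. At 1.8 cm/year, the penalty used for the FDA/PMDA sensitivity analysis in section 10.1, about 92% survive the first and 81% the second.

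**The case against.** A reader might infer that somapacitan-only is wrongly labelled the most conservative evaluation. The documents do not support that. The phrase ranks the plan's own three scenarios in order to set the δ range, and the ranking is algebraically right. The label misleads only if read as the worst case over all departures.

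A reader might also infer that two scenarios pass a test by construction. The plan sets no pass/fail rule for them. It runs one tipping search, on the somapacitan-only case, and calculates the other two over the same range. That search is genuine. It remains true that the other two lines cannot supply adverse evidence.

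The direction is not arbitrary: lack of efficacy is a reasoned ground for positive δ. But the argument is conditional, and the plan does not show that the condition holds in either arm.

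Opposite departures are already examined under the FDA/PMDA estimand for the same endpoint and margin. That is partial cover, because the missing set is smaller and the estimand differs.

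Finally, the halving of the tipping value follows from splitting the same total shift between two arms, so it does not by itself show that robustness is overstated. At an estimate of 0, the opposite departure needed (3.43 per arm) slightly exceeds the 3.3 cm/year that section 5.4 takes as the growth hormone effect against no treatment. Both points stand, and they limit the weight of the concern.

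**Conclusion.** The point holds as incompleteness. For EMA, the Norditropin-only scenario can never overturn non-inferiority, and the equal-departure scenario cannot do so within the planned range unless f0 = 0. Departures in which missing Norditropin children grow more, alone or with a somapacitan penalty, are not examined.

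The consequence is small if the estimate is near or above 0. It matters in a close result: at an assumed estimate of -0.5, somapacitan-only just survives a 1.8 cm/year departure (tipping at 1.85), while opposite departures tip at 0.93.

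These values rest on the planning SD, 10% unobserved in each arm, the plan's fixed standard error, and a t-based interval in place of the MMRM. The estimates of 0 and -0.5 and the unequal fractions are illustrative. The primary non-inferiority decision does not change.

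**What to change.** Keep the three scenarios and add a two-dimensional analysis under the plan's own sign convention: subtract Δ = f1·δ1 - f0·δ0, with δ1 ≥ 0 and δ0 allowed below 0 (negative δ0 means that missing Norditropin children grow more than observed ones). Report the (δ1, δ0) boundary at which the 95% CI crosses -1.8 cm/year. The existing scenarios are the lines δ0 = 0, δ1 = 0 with δ0 ≥ 0, and δ1 = δ0, so nothing planned is lost, and EMA then matches the c and b analysis for FDA/PMDA. Reword the label to say that somapacitan-only is the most conservative of these three scenarios.

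The cost is one paragraph and a closed-form calculation, with no new data. The downside is that the reported tipping values may look less favourable.

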10.3.2 Secondary endpoints

Confirmatory secondary endpoints

N/A

Supportive secondary endpoints

Effect

Change from screening (visit 1) to visit 7 (week 52):

- Bone age (years)

Change from baseline (week 0) to visit 7 (week 52):

- Height SDS (-10 to +10)
- Height Velocity Standard Deviation Score (HV SDS) (-10 to +10)

The effect endpoints will be analysed based on the ‘in-trial’ observation period within the main trial period (52 weeks of treatment).

Height SDS will be derived using Centre for Disease Control and Prevention (CDC)¹⁷ standards and HV SDS will be derived using Prader standards as reference data.

The time interval used for the derivation of baseline HV is defined as: from date of pre-trial height assessment (a minimum of 6 months and maximum of 18 months prior to screening) to date of randomisation visit.

Change in height SDS and HV SDS will be analysed using the same analysis model as was used for analysing the primary endpoint for the primary estimand (treatment policy strategy) except for using baseline height SDS and baseline HV SDS, respectively, as a covariate in the model instead of baseline height. The estimate for the treatment difference at week 52 will be reported with corresponding 95% CI and p-value.

Change in bone age will be analysed using an ANCOVA model on change in bone age/chronological age assessed at week 52 and the model will include treatment, gender, age group, region, GH peak group and gender by age group by region interaction term as factors and bone age/chronological age at screening as a covariate. The treatment difference estimate will be reported with corresponding 95% CI and p-value. Subjects without post-randomisation data for the analysed endpoint will not be included in the analysis.

Safety

Change from screening (visit 1) to visit 7 (week 52):

- Fasting plasma glucose (mmol/L)
- HOMA (%)
- HbA_{1c} levels (% points)

HOMA will be reported as steady state beta cell function (HOMA-B) and insulin resistance (HOMA-IR). The safety endpoints will be analysed using descriptive statistics based on the ‘on – treatment’ observation period and the ‘in-trial’ observation period.

Pharmacodynamics

Change from baseline (week 0) to visit 7 (week 52):

- IGF-I SDS (-10 to +10)
- IGFBP-3 SDS (-10 to +10)

The PD endpoints will be analysed based on the ‘on-treatment’ observation period and the ‘in-trial’ observation period.

Change in IGF-I SDS and IGFBP-3 SDS will be analysed using a MMRM with an unstructured covariance matrix on all relevant post-baseline change from baseline values as dependant variables. The model will include treatment, gender, age group, region, GH peak group and gender by age group by region interaction term as factors and baseline value as a covariate, all nested within week as a factor. From the MMRM, the treatment difference at Week 52 will be estimated and the corresponding 95% CI and p-value will be reported for each endpoint. Subjects without post-randomisation data for the analysed endpoint will not be included in the analysis.

10.3.3 Exploratory endpoints

The exploratory endpoints will be analysed based on the ‘on-treatment’ observation period. TB-CGHD-O and TB-CGHD-P scores will be analysed using a MMRM with an unstructured covariance matrix on all relevant post-baseline values as dependant variables. The model will include treatment, gender, age group, region, GH peak group and gender by age group by region interaction term as factors, all nested within week as a factor. From the MMRM, the treatment differences will be estimated and the corresponding 95% CI and p-values will be reported for week 26 and week 52, respectively. Changes from baseline to week 26 and week 52 in TRIM-CGHD-O scores will be analysed using a MMRM with an unstructured covariance matrix. The model will include treatment, gender, age group, region, GH peak group and gender by age group by region interaction term as factors and baseline value as a covariate, all nested within week as a factor. From the MMRM, the treatment differences will be estimated and the corresponding 95% CI and p-values will be reported for week 26 and week 52, respectively. G-DAT and PPQ data will be analysed using descriptive statistics.

10.3.4 Reporting of the main part of the trial

Data for all subjects up to and including Visit 7 will be included in an interim database lock. At this interim DBL the sponsor will become unblinded regarding the somapacitan vs Norditropin[®] allocation during the main trial period. The results from the main part of the trial is planned to be used as basis for regulatory filings.

10.3.5 Other analyses

Adverse events will be analysed using descriptive statistics based on the ‘on –treatment’ observation period (primary evaluation) and ‘in-trial’ observation period (secondary evaluation) within the main trial period (52 weeks of treatment). The adverse events will be summarised by treatment, MedDRA (Medical Dictionary for Regulatory Activities) system organ class and MedDRA preferred term. The descriptive statistics will include the number and percentage of subjects who experienced adverse events, the number of events and rate. Adverse events will be listed by treatment and subject with information on severity, relationship to trial product and demographics based on the ‘on –treatment’ observation period. Adverse events with onset 14 days or more after last trial drug administration will be reported in a separate listing. Adverse events with onset before first dosing will be reported in a separate listing.

Similar tables will be made for adverse events in the extension trial period.

10.4 Pharmacokinetic and/or pharmacodynamic modelling

Somapacitan and IGF-I serum concentration data will be used for population PK, population PK/PD and exposure-response modelling, potentially as a joint analysis of data from multiple trials. Other exploratory PK/PD and exposure-response analyses for this trial may be performed if deemed

Protocol
Trial ID: NN8640-4263

~~CONFIDENTIAL~~

Date:	22 February 2021	Novo Nordisk
Version:	7.0	
Status:	Final	
Page:	55 of 94	

relevant. A more technical and detailed elaboration of the population PK, population PK/PD and exposure-response analyses will be given in a prospective modelling analysis plan.

11 References

1. The European Parliament and the Council of the European Council. Directive 2001/20/EC of the European Parliament and of the Council of 4 April 2001 on the approximation of the laws, regulations and administrative provisions of the member states relating to the implementation of good clinical practice in the conduct of clinical trials on medicinal products for human use. 2001.
7. Rosenfeld RG. Growth hormone deficiency in children. *Endocrinology (Degroot LJ, Jameson JL, Eds), 4th edition, W B Saunders.* 2001:503-19.
8. GH Research Society. Consensus guidelines for the diagnosis and treatment of growth hormone (GH) deficiency in childhood and adolescence: summary statement of the GH Research Society. GH Research Society. *Journal of Clinical Endocrinology and Metabolism.* 2000;85(11):3990-3.

Appendix 1 Abbreviations and Trademarks

ADA	anti drug antibodies
ADHD	Attention deficit hyperactivity disorder
AE	adverse event
BIA	bioelectrical impedance analysis
CRF	case report form
CT	computerised tomography
CTR	clinical trial report
DFU	directions for use
DMC	data monitoring committee
DUN	dispensing unit number
eCRF	electronic case report form
ECG	Electrocardiogram
EMA	Euoropean Medicins Agency
FAS	full analysis set
FDA	U.S. Food and Drug Administration
FDAAA	FDA Amendments Act
G-DAT	growth hormone device assessment tool
GH	growth hormone
GCP	Good Clinical Practice
GHD	growth hormone deficiency
HbA _{1c}	glycated haemoglobin
hGH	human growth hormone
HOMA	homeostatic model assessment
HV	height velocity
IB	investigator brochure
ICH	International Council for Harmonisation
ICMJE	International Committee of Medical Journal Editors
IEC	independent ethics committee
IGF-I	insulin-like growth factor I
IGFBP-3	insulin-like growth factor binding protein 3
IMP	investigational medicinal product
IRB	institutional review board
IWRS	interactive web response system

LAR	legally acceptable representative
MI	multiple imputations
MMRM	mixed model for repeated measurements
MRI	magnetic resonance imaging
PCD	primary completion date
PD	pharmacodynamics
PK	pharmackinetics
PP	per protocol
PPQ	patient preference questionnaire
PRO	patient reported outcome
RNA	ribonucleic acid
SAE	serious adverse event
SAP	statistical analysis plan
s.c	subcutaneous
SDS	standard deviation score
SGA	Small for gestational age
SUSAR	suspected unexpected serious adverse reaction
TB-CGHD-O	treatment burden-child growth hormone deficiency-observer
TB-CGHD-P	treatment burden-child growth hormone deficiency-parent
TMM	trial materials manual
TRIM-CGHD-O	Treatment Related Impact measure-Child-Growth Hormone Deficiency-Observer

